With no Class I randomized, prospective, blinded treatment trials of PTH, some clinicians have used migraine-specific therapy for PTH based on anecdotal evidence of success. Erickson et al conducted a retrospective review of PTH treatment in a clinic-based population of active duty soldiers, and found that the “triptans”, a class of migraine-specific medications, were effective in those suffering from moderate to severe PTH, both blast and non-blast related.⁵⁶

Most, but not all, of these headaches had migraine characteristics. A breakdown of reported effectiveness did not specifically correlate headache characteristics with drug responsiveness.

The rationale for treatment with migraine specific therapy is that though primary headache disorders may be due to an inherited disorder of transmission resulting in episodic brain dysfunction and PTH is thought to have a structural basis or potentially treatable cause relating to an injury, both may have a similar response to migraine-specific treatment based on a similar phenotype. Therefore, in moderate to severe PTH meeting classification criteria for migraine or probable migraine, the use of triptans has been thought to be a reasonable course of action.

However, no research has been conducted on triptans in PTH to determine whether there may be different side effect profiles from primary migraine treatment or whether the medication can be taken appropriately (for example, that it has greater efficacy when taken at headache onset) by individuals with TBI.

Why triptans? Pharmacological features of triptans and the concept of the physiological “common pathway”: Migraine specific medications include the “triptans” which are serotonin 5-HT 1B/1D agonists that work to inhibit inflammatory peptide release (e.g., calcitonin gene-related peptide, CGRP, a potent vasodilator) in the meninges through the serotonin 1D receptor. Blocking release decreases a “pain signal” being generated from peripheral trigeminal nerves to the trigeminal nucleus caudalis which is thought to modulate or generate migraine. Triptans also bind to receptors on the meningeal artery endothelium via serotonin 1B (5-HT 1B) receptors causing vasoconstriction of vessels dilated by CGRP or other inflammatory peptides.

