4. Evaluate the ability of persons with TBI, and their caregivers as indicated, to successfully use abortive headache medications and comply with treatment.
5. Examine the relationship between PTH and cognitive, emotional, and other self-report measures to determine important factors to include in a Phase III study.

VI. Overview of Study Design

This phase II evaluation of sumatriptan as a treatment for PTH will examine the methods and approach necessary to take the next step to a phase III trial. The sample will include 40 individuals with mild (with adequate documentation or in the opinion of study physician), moderate and severe TBI who will be recruited primarily from patients within UWTBIMS and from outpatient clinics and brain injury related organizations to be followed over 3 months. We plan to enroll individuals with moderate to severe headache who experience at least two and up to a maximum of fifteen moderate to severe headaches per month. **Severity will be rated using a 4 point pain scale (0=no headache, 1=mild headache, 2=moderate headache, 3=severe headache).** Headache classification will be confirmed by clinician interview.

Table 1. Summary of Protocol for Proposed Study of Sumatriptan for PTH

Pre-Screening	Visit 1 (Day 1)	Days 1-29	Visit 2 (Day 30)	Days 31-89	Visit 3 (Day 90)
Inclusion/ Exclusion Criteria	Consent Headache questionnaire All subjects trained in use of headache diary	Daily headache diary Weekly telephone calls Daily headache diary reminders (phone, text, email)	Evaluate headache diary for eligibility (pre-visit) Baseline assessment (if meets headache diary eligibility) History, clinical headache interview and physical examination Dispense drug if eligible	Daily headache diary Study drug use per instruction Weekly telephone calls	Follow up Assessment Drug count

Population

A. Inclusion criteria:

A subject will be eligible for enrollment into this study if all of the following criteria are met:

- Age 16-65. The higher age limit is set to 65 to reduce likelihood of health issues which may be a contraindication to the use of sumatriptan and to meet recommendations by the International Headache Society.⁶²

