- Diagnosis of mild (with adequate documentation or in the opinion of study physician), moderate or severe TBI occurring at least 2 weeks but not greater than 60 months before enrollment. Two weeks was chosen to include only those subjects who are having headache beyond their acute injury and 60 months was chosen to ensure that the headache may reasonably be connected to the TBI.
- Subject has at least two and up to a maximum of fifteen total moderate to severe headache days per month. Subject report of meeting this criterion will result in the subject entering the first month of the study. However, this frequency must be documented in headache diary to enter the treatment phase of the study.
- Headaches are classified as moderate to severe (2 or 3 on the 4 point pain scale: 0=no headache, 1=mild headache, 2=moderate headache, 3=severe headache). As above, headache severity must be documented in the month-long headache diary prior to entry into the treatment phase.
- Subject obtains a score of 25 or greater on the Mini Mental Status Examination⁶³ or has a caregiver to monitor implementation of study procedures including the headache diary and medication regimen.

- Subject is able and willing to give written informed consent for participation in screening activities and to participate fully in the study if eligible. For those subjects who score below 25 on the Mini Mental Status Examination, there must be a caregiver willing to also be consented for participation in the study.
- Female subjects of childbearing potential must have a negative pregnancy test at enrollment, and agree to remain abstinent or use acceptable methods of birth control (i.e., hormonal contraceptives, intrauterine device, diaphragm with spermicide, cervical cap or sponge, condoms, or partner has had a vasectomy). Sumatriptan has been assigned to pregnancy category C by the FDA. Animal studies have revealed evidence of decreased fetal body weight, embryo lethality, and cervicothoracic vascular defects. There are no controlled data in human pregnancy and therefore, sumatriptan should only be given during pregnancy when benefit outweighs risk.

B. Exclusion criteria:

A subject will not be eligible to participate in this study if any of the following criteria apply:

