Pre-treatment Visit (*Visit 1*): Subjects who complete informed consent and meet the inclusion criteria (with no exclusion criteria) will be asked to complete 30 days of headache diary questions. This will document the number of headaches, headache severity, headache days and description of their headache and associated symptoms. This will assist in determining compliance and ability to complete this portion of the study, and ensure that the frequency of headaches is sufficient to include into study intervention (See Attachment 9 Study Sequence Flow Sheet). Research staff will meet with the subject (and caregiver) to provide training on headache diary utilization and will contact them on a daily and/or weekly basis to answer questions and maximize accuracy and compliance with the diary, depending on the subject's preference. Proper utilization of a headache diary and success of data input by the subject and caregiver will be evaluated following weekly interviews with the research assistant. The

headache diary will be available in multiple forms. We will have iPod Touch devices loaded with a headache diary application that will allow for direct entry of responses onto a security protected survey site and will include reminders for daily completion as well as prompts for efficacy of drug treatment used. However for those who prefer, a computer accessed web-based headache diary (otherwise similar to the iPod version) and a paper version with identical questions will be available. For those who choose the alternate forms of diary, a clip-on timer will be provided for recording of headache duration and reminders may be sent as text messages or emails based on subject preference.

Treatment Visit (*Visit 2*):

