Use of sumatriptan and rescue drug: Two packages of nine (9) sumatriptan 100- mg. pills (18 pills total for 2 months of treatment) will be dispensed to each subject on Day 30 once they have gone through baseline assessment. On average, this will treat a minimum of 5 headaches or a maximum of 9 headaches per month. Subjects will be instructed to take the sumatriptan at the onset of headache pain. If subjects are not pain free at 2 hours after the first dose of study medication, they will be allowed to take one additional pill, but will be limited to 2 pills in a 24 hour period. Subjects will be instructed to take no more than 9 pills in a 30 day period based on research which suggests that additional dosages may increase the risk of medication-overuse headache. A list of appropriate medications will be provided that they can use if they: 1) continue to have headache pain 2 hours after their second dose of study drug, or 2) they have used their 30 day supply of study drug within the month. All subjects will be contacted by telephone on a weekly basis to review their headache diaries, assess potential adverse events, review compliance with use of the study drug, assess other treatments being utilized, and answer any questions. After 60 days, all subjects will be given an outcome assessment. The measures included in this assessment are shown in Table 2.

Compliance: Compliance will be assessed during the weekly telephone follow-up calls to subjects and caregivers and we will have subjects return their medication packs and any unused medication at Visit 3. Any lack of compliance to the study protocol will be recorded on case

report forms for that subject. Subjects will be encouraged to improve compliance and the research staff will assist the subject and/or caregiver in problem solving compliance issues, including suggesting to subjects that staff contact them either via email, telephone or text with daily reminders to complete their headache entry.

Medication administration: The study drug will be distributed in blister packs. Subjects will be instructed to decrease the dose by 50% (cut the tablet in half) if side effects occur after the first dose. They will also be required to contact the research staff to report the side effects. If the side effects continue to be intolerable, that subject will be discontinued from the intervention portion of the study but will be asked to continue keeping their headache diary.

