Rationale for Dosage Selection and Medication Administration Procedures: The recommended initial dosage of Sumatriptan is 100 mg⁷⁶ and this is the most commonly prescribed dose in primary care as well as neurology or headache specialty clinics. In a meta-analysis of 53 clinical trials involving sumatriptan,⁷⁷ 100 mg of Sumatriptan resulted in 29% of patients becoming pain free at 2 hours (moderate to severe pain to no pain) vs. placebo. This is a much more rigorous end-point than the pain relief response which showed a 59% headache relief response (moderate to severe to mild or no pain) vs. placebo. Rescue medications will include acetaminophen, ibuprofen, or other analgesic as prescribed by the subject's own physician; detailed instructions will be provided to the subjects.

A. Subject Discontinuation: Subjects may be discontinued from the study drug by their request or if the subject experiences an adverse effect sufficient to warrant withdrawal

from the study drug. In the case of discontinuation of study drug, the reason will be recorded and the subject will be asked to continue to monitor their headaches with use of the headache diary and to participate in a final assessment.

Compensation: Subjects will be given \$25 upon completion of each of the three clinic visits (total \$75). This compensation is to defray the cost of phone use, transportation/parking cost, and any meals and to compensate subjects for their time. Subjects will also have their parking costs validated.

X. Data Analysis

Study Sample Size and Rationale: This is a single arm, unblinded study and is being undertaken to test necessary study instruments and procedures, establish feasibility and determine side effects in a population with mild (with adequate documentation or in the opinion of study staff) moderate, or severe TBI in preparation for a subsequent Phase III study. Therefore, we are using forty subjects as a reasonable sample size to meet these aims.

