Case Availability: We anticipate no difficulty in recruiting 40 subjects to participate. Given our natural history study,¹⁹ we expect at least 48% of TBIMS subjects to have headaches that qualify in terms of both frequency (4 to 15 headaches per month) and severity (rating of 2 or 3 on the 4 point scale), (26% had qualifying headaches at 3 months, another 10% who did not qualify at 3 months had qualifying headaches at 6 months and another 12% who had not qualified previously had qualifying headaches at 12 months). The UWTBIMS expects to

recruit at least 45 patients per year. Those entered in the first 3.5 years of the upcoming cycle ($45 \times 3.5 = 158$ TBIMS participants) will be eligible for the headache study. Additionally, because eligible subjects can be between 3 and 60 months post-injury at recruitment, we will be able to contact the UWTBIMS subjects enrolled in the previous 60 months who indicated interest in being contacted for future studies.

Data Analysis: Data analysis for the feasibility and safety aims will be primarily descriptive. We will calculate the percent of subjects who used the diary successfully, percent who stopped taking sumatriptan because of side effects, percent who experienced each adverse event, and percent who were able to maintain compliance with treatment. We will present a confidence interval for each estimate. To get preliminary data on efficacy of sumatriptan, we will compare headache control before and after the participants start taking sumatriptan. We will calculate the percent of headaches that had complete resolution (pain free at 2 hours) for each person, during the initial (pre-intervention) month when they used their regular treatment and during the two months (intervention) when they treated headaches with sumatriptan and compare them using a paired t-test. We will also examine different definitions of headache relief (pain free by 30 minutes, no more than mild pain (score ≤ 1) by 30 minutes, no more than mild pain by 2 hours) to see if another outcome measure may have advantages for a future Phase III study. We will descriptively examine any differences in compliance, side effects, and feasibility based on cognitive functioning, as well as by other self-report and emotional health measures. Changes in these measures from pre to post

treatment will also be examined to determine whether there is any change that occurs with treatment and which may be important variables to include in a Phase III study.

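### Two of the three exploratory relief definitions in section X set no starting severity, so as written a headache already mild at treatment counts as relieved without any change

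*Combined protocol and SAP*

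**What the plan says.** Section X computes, for each subject, the percentage of headaches with no pain at 2 hours, and compares the diary month with the two treatment months by a paired t-test. It then lists three alternative definitions, to see whether one would serve better in Phase III: no pain by 30 minutes, and "no more than mild pain (score ≤ 1) by 30 minutes, no more than mild pain by 2 hours". No score at treatment is attached to any of them, and the percentage is taken over headaches without a severity filter.

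Five other places bear on how these read:

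- Section VI (Overview of Study Design) sets the scale: 0 is no headache, then "1=mild headache, 2=moderate headache, 3=severe headache".
- Section IX (Use of sumatriptan and rescue drug): "Subjects will be instructed to take the sumatriptan at the onset of headache pain". No severity threshold is given.
- Population, A. Inclusion criteria, requires moderate to severe headaches, and "headache severity must be documented in the month-long headache diary prior to entry into the treatment phase". This is a condition for a subject to enter treatment.
- Section IX (Rationale for Dosage Selection) cites a meta-analysis with a "59% headache relief response (moderate to severe to mild or no pain) vs. placebo". That form does state a starting severity.
- Section X describes the comparison period as the one "during the initial (pre-intervention) month when they used their regular treatment". When in a headache that treatment is taken is not specified.

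**The concern.** Relief normally means that pain fell. Under these two definitions a headache scored 1 at dosing and still scored 1 later is a success, although nothing changed. The measures also differ from the form of relief that the protocol itself cites from the meta-analysis, so the two rates cannot be compared directly.

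Two consequences follow. First, the level of relief rises whenever mild headaches stay at 1 or below more often than moderate or severe ones fall to 1 or below. Second, the before/after difference depends on the severity mix at treatment. The instruction to treat at onset covers study drug only, so the share of headaches mild at treatment may differ between the diary month and the treatment months. The documents do not show whether it does.

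At stake is the choice of a Phase III outcome and, through Aim 2, the effect size used to plan that trial. A measure that partly records how early the subject treated cannot be compared fairly with the pain-free measures.

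**Working it through.** The plan gives no figure for these measures, so there is none to reproduce.

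**Step 1: apply each definition to a score that does not change.**

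| Score at treatment and later | No pain | Score ≤ 1 |
|---|---|---|
| 1 | not met | met |
| 2 | not met | not met |
| 3 | not met | not met |

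Exactly two of the three exploratory definitions are met without change, namely score ≤ 1 by 30 minutes and by 2 hours. No pain by 30 minutes and the primary outcome are not.

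**Step 2: can headaches scored 1 enter the calculation?** Yes. Dosing is at onset with no threshold, the percentage is over all headaches, and the 2-or-3 rule decides which subjects are treated. A qualifying subject may also have mild headaches.

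**Step 3: what the measure estimates.** For one subject's headaches in one period, let m be the share mild at treatment, s the share of those that stay ≤ 1, and r the share of moderate or severe headaches that fall to ≤ 1. Then

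observed relief = (1 − m)·r + m·s.

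Of m, s and r the documents supply only a possible value for r, the cited 59%. Every other value below is an assumption chosen for illustration.

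**Step 4: level.** Take r = 0.59, reading the cited 59% as a response rate (itself an assumption).

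- m = 0.20, s = 0.80: 0.80 × 0.59 + 0.20 × 0.80 = 63.2%.
- m = 0.30, s = 1.00: 0.70 × 0.59 + 0.30 × 1.00 = 71.3%.

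A true 59% would read as 63.2% to 71.3% over that range.

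**Step 5: difference with the same mild share in both periods.** The difference is (1 − m)·Δr + m·Δs. Let r rise from 35% to 50%, a true gain of 15 points.

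| s before → after | m = 20% | m = 30% | m = 50% |
|---|---|---|---|
| 90% → 90% | 46.0 → 58.0 = 12.0 | 51.5 → 62.0 = 10.5 | 62.5 → 70.0 = 7.5 |
| 75% → 90% | 43.0 → 58.0 = 15.0 | 47.0 → 62.0 = 15.0 | 55.0 → 70.0 = 15.0 |
| 70% → 90% | 42.0 → 58.0 = 16.0 | 45.5 → 62.0 = 16.5 | 52.5 → 70.0 = 17.5 |

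The gain is diluted only if Δs < Δr. It is unchanged if they are equal and enlarged if Δs > Δr. Δs = 0 cannot be taken for granted: section IV raises, in passing, that "it has greater efficacy when taken at headache onset".

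**Step 6: difference when the mild share shifts and nothing else changes.** With r and s the same in both periods, the difference is (m₁ − m₀)·(s − r). Take r from 20% to 50% and s from 80% to 100%.

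- 10-point shift: from 0.10 × (0.80 − 0.50) = 3 points to 0.10 × (1.00 − 0.20) = 8 points.
- 5-point shift: half of that, 1.5 to 4 points.

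The sign follows the direction of the shift.

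**The case against.** The strongest reply is that a state reached, rather than a fall, is a sensible outcome under early treatment. A headache treated at 1 that stays at 1 may have been kept from getting worse, and section IV reports that triptans are recommended whatever the pain level. Restricting relief to scores of 2 or 3 would remove those headaches from the measure. This has force. It is a reason to report them on their own, not to pool them with headaches that actually improved.

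Second, a change in severity mix also affects the pain-free measures, including the primary outcome. That is true of the mix in general. Only the two measures discussed here, however, can be met at time zero.

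Third, the consequence is not demonstrated. The shares are assumed, the direction is open, and the remark in section IV about onset is brief and gives no comparison by severity. All of this stands, and the figures above should be read only as illustrations.

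Fourth, diary content is in Attachment 19, with a flow chart in Appendix A; neither was available. Section VIII (Visit 1) says the application has "prompts for efficacy of drug treatment used", and these may record severity at treatment. If so, the fix is easy, but the definitions in section X remain as written. The post-dose items listed under Subject Instruction do not name the score at dosing.

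Finally, these are exploratory measures in a 40-subject, single-arm feasibility study, with no decision rule attached. That limits the priority.

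**Conclusion.** The point holds for the wording of section X. Followed literally, two of the three exploratory definitions count an unchanged mild headache as relieved, and no other section reviewed limits the analysed headaches to a score of 2 or 3 at treatment. This much is certain from the text.

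The effect on the results is uncertain in size and sign. It depends on the share of headaches mild at treatment in each period and on how those headaches behave, and the documents report neither. If almost no headaches are treated at score 1, the effect is negligible. With a substantial share, a distortion of several points in either direction is plausible.

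The correction should be made because it is cheap and the measures are intended to guide the Phase III outcome. It does not threaten the primary outcome or the feasibility and safety aims.

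**What to change.** In section X:

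- Define relief as a score of 2 or 3 at treatment falling to 1 or 0, by 30 minutes and by 2 hours. An unchanged mild headache then leaves the measure, and the observed rate equals r whatever m is.
- Report headaches treated at score 1 separately, as the share that become pain free and the share that progress to 2 or 3.
- Tabulate severity at treatment in the diary month and in the treatment months. Do not rely on the 2-or-3 subset alone, because treating at onset may change which headaches fall into it.
- For diary-month headaches with no medication taken, state the reference time and score used (for example, severity at onset), or report them separately.

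Use the score at treatment from the diary. Add that item only if Attachment 19 does not already capture it in both periods; if it is not recorded at the time, it cannot be recovered reliably later. Dosing instructions are not affected.

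The cost is a few sentences, possibly one diary item, and some precision. Section IX expects drug supply for roughly 5 to 9 headaches a month, so the restricted measure rests on fewer headaches per subject. A subject with none treated at 2 or 3 in a period has no relief percentage for that period and drops out of the paired comparison on that measure; the number of such subjects should be reported.
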